(v) *Patient randomization.* Randomization will be performed as we have previously published. To keep birth-weight distribution comparable in the two groups, we will use five 250-gram-birth weight strata for randomization. To ensure equal enrollment in the two groups, infants will be randomly assigned within each stratum, according to a permuted block design to receive inhaled nitric oxide (INOmax®, INO Therapeutics) or

oxygen placebo. This strategy provides a balanced group assignment with every 4 enrollments.

(vi) *Patient enrollment at study entry procedures.* We will enroll patients and enter them into the study as we have previously published. Briefly, potential subjects will be identified, prenatally if possible, and the parents approached for informed consent. With consent obtained, and the infant born, admitted, and verified to meet inclusion criteria, a sealed envelope containing the randomized treatment assignment, appropriate identifying labels, etc., will be pulled and opened by the respiratory therapist. Documentation of the treatment assignment and patient data will be recorded by the respiratory therapist in the study book (kept in the respiratory therapy room), and an INOvent® brought to the bedside. The INOvent will be set to deliver either iNO or oxygen according to the treatment randomization and then covered to conceal the treatment group from the caregivers and investigators.

(vii) *Treatment.* iNO or placebo (oxygen) will be given 5 ppm while ventilated or on continuous positive airway pressure (CPAP) and 10 ppm while on nasal cannula oxygen. In infants receiving iNO by nasal cannula, iNO concentrations are set to 10 ppm, because previous studies have shown that delivery 10 ppm by nasal cannula results in nasopharyngeal concentrations of about 5 ppm^9. These dosages will continue until the infant no longer needs supplemental oxygen or reaches 33 weeks post conceptional age. All infants will have iNO delivery devices (INOvents) at the bedside to deliver either iNO or O2, and will be shrouded to hide from caregivers the nature of the gas being delivered. Only respiratory therapy and data safety monitor to know of gas assignments.

(viii) *Data Collection.* Clinical data (fluids, medications, diagnoses, ventilator settings) will be collected daily by our research professional.

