(ix) *Sample size.* In our previous study of infants with RDS, iNO treatment cut the risk of abnormal neurodevelopmental outcome by half. The baseline incidence of abnormal neurodevelopmental outcome is 40% in this age group by published NICHD data. Therefore to see a decrease of abnormal neurodevelopmental outcome to 20% (half of baseline incidence) with 80% power, 82 babies are needed in each arm of the study, for a total of 164 babies. We have previously published an overall mortality rate for intubated infants < 2000g in our nursery of 23%. Because we are including non-intubated infants, we

estimate a mortality rate of about 18%. Therefore, to ensure sufficient infants surviving to follow up, we anticipate needing to enroll approximately 215 babies over 18 months. With a historic 80% follow-up rate, we will need a total of 268 infants. Every year we admit approximately 175-200 infants with birth weights < 1500g. We therefore anticipate enrollment taking as long as 18 months. Our non-consent rate historically is < 10%.

(x) *Standards of neonatal intensive care.* Because we have shown no effect of ventilatory strategy on neurodevelopmental outcome, there will be no external control of ventilatory modality. Because this is a single-site study, variability in practice exists only between our eight member group of neonatologists, with constant care provided by nurse practitioners, residents, and nursing staff.

(xi) *Safety monitoring.* As per our clinical routine, methemoglobin is regularly monitored with arterial blood gases. Although we and others have shown that iNO therapy is safely used in preterm infants, interim safety analyses will be performed when 50% of patients enrolled. Deaths will be compared, as will the incidence of severe intraventricular hemorrhage, and tests of significance made with Chi-square. The study will be stopped if the incidence of either index in the iNO groups is significantly higher than in placebo groups.

(xii) *Primary Outcome.* As we have published, we will measure abnormal neurodevelopmental outcome at 18 months corrected age. Three disability levels will be assessed: disability (cerebral palsy, blind in both eyes, or deaf in both ears); delay (score on Mental or Psychomotor Developmental Index of the Bayley Scales of Infant Development < 70 without a disability) or normal (without disability or delay).

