(xv) *Assessment of neurodevelopmental outcome.* As we have previously published, at 18 months post conceptional age, developmental screening with Bayley exams will be performed in our High Risk Follow-up Clinic by [name], who will also perform neurological examinations to identify those infants with cerebral palsy. Other assessments will include measurements of physical growth and review of routine visual and hearing examinations to determine blindness or deafness. Questionnaires assessing socioeconomic status and self report of racial ethnicity will be administered. All examiners will be unaware of treatment regimen assignment. In our previous studies, our follow-up rate of >80% is very high by published standards, especially for an inner city community such as we serve. We anticipate that rate will continue for the current study.

(xvi) *Data analysis.* As we have previously published, data will be analyzed as "Intent to Treat." . Clinical and demographic variables between groups will be compared with Fisher's exact test for categorical variables and Wilcoxon rank-sum tests for continuous variables. Primary outcomes will be analyzed with generalized linear models to obtain relative risks of primary outcome in the two groups. Effects of potential confounders will be adjusted for in the model: birth weight, sex, socioeconomic status, as well as for potential the intermediate variables: prolonged exposure to postnatal steroids, presence of chronic lung disease, severe IVH, or periventricular leukomalacia (PVL). Further analyses of Bayley scores, both cognitive (MDI) and psychomotor (PDI) will be performed.

(xvii) *Anticipated results and critique.* We anticipate that infants treated with iNO will demonstrate significantly decreased incidences of abnormal neurodevelopmental outcomes and will also demonstrate significantly increased cognitive abilities, as demonstrated by MDI scores. We further anticipate that these effects will persist after statistical adjustment for factors independently predisposing to abnormal neurodevelopmental outcome, such as male gender and gestational age, as well as adjustment for factors potentially mediating adverse neurodevelopmental outcome, such as chronic lung disease, intraventricular hemorrhage, or PVL.

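### Twins and triplets can enrol but are analysed as unrelated infants: a small, free gain in precision is missed for the primary outcome, and standard errors in the Aim 2 regressions may be somewhat too small.

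*Combined protocol and SAP*

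**What the plan says.** All places are in the Combined protocol and SAP, RESEARCH PLAN.

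- **Eligibility (Specific Aim #1, iii and iv).** Every premature infant who meets the age, weight and respiratory-support criteria can enter. The exclusions cover anomalies, genetic syndromes, non-viability and very severe lung disease. Multiple births are not mentioned.
- **Randomisation (Specific Aim #1, v).** "we will use five 250-gram-birth weight strata for randomization", and "infants will be randomly assigned within each stratum, according to a permuted block design", balanced after every 4 enrolments. The unit is the infant. No rule for siblings is given.
- **Sample size (Specific Aim #1, ix).** The target is "to see a decrease of abnormal neurodevelopmental outcome to 20% (half of baseline incidence) with 80% power", giving "82 babies are needed in each arm of the study, for a total of 164 babies".
- **Primary analysis (Specific Aim #1, xvi).** "Primary outcomes will be analyzed with generalized linear models to obtain relative risks of primary outcome in the two groups". The covariates are birth weight, sex, socioeconomic status and several intermediate variables. No family term, clustering or robust variance is named.
- **Aim 2 analysis (Specific Aim #2, vii).** Arterial-venous (A-V) differences and cGMP are compared between arms by ANOVA and also related to each infant's neurodevelopmental outcome by regression, again with no family term.

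**The concern.** A nursery that takes all comers under 1500 g can be expected to enrol twins and triplets. Siblings share gestation, mother and household, and the Background section on neurodevelopmental outcomes names prematurity and socioeconomic status as determinants of outcome. Their outcomes are therefore likely to be correlated, while an ordinary generalized linear model assumes that they are not.

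The consequence depends on how siblings are spread over the arms. Siblings in opposite arms give a within-family comparison that an independence model does not exploit. Siblings in the same arm carry less information than the model assumes. In Aim 2 the exposure is a blood measurement, so randomisation of the gas does not protect the regression standard error.

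**Working it through.** **1. The plan's own figure.** Inputs are 40% v 20% and 80% power, from the sample-size section. Alpha is not stated, so two-sided 0.05 is assumed.

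n = [1.96√(2×0.3×0.7) + 0.842√(0.4×0.6 + 0.2×0.8)]² / 0.2² = 81.2, so 82 per arm, with 80.4% power. The figure reproduces exactly as the independent-infant calculation.

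**2. Assumptions.** Let f be the share of analysed infants in twin pairs, ρ the within-pair outcome correlation, and a the probability that both twins get the same gas. I take f = 20-40% and ρ = 0.2-0.6, with f = 0.3 and ρ = 0.4 as the central case. Triplets are not modelled.

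**3. Same-gas probability under the written scheme.** Two twins in the same block of 4 are split with probability 2/3. Two consecutive enrolments in one stratum share a block 3/4 of the time and otherwise are split half the time: 0.75×2/3 + 0.25×1/2 = 62.5%. Twins in different strata are split about half the time. So a lies between 1/3 and 1/2.

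**4. Validity of the ordinary primary analysis.** Design effect = 1 + fρ(2a − 1).

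- Central case: 0.96 (a = 1/3), 0.97 (a = 0.375), 1.00 (a = 1/2).
- The ordinary standard error is therefore right, or up to about 2% too wide (1/√0.96 = 1.021).
- A simulation of 164 infants in five strata with blocks of 4 (8,000 runs, no true effect) agrees. At f = 0.3, ρ = 0.5 the mean ordinary standard error was 0.0760 against a true 0.0759, with type I error 4.7%. At f = 0.4, ρ = 0.7 it was 0.0760 against 0.0738, with type I error 4.1%.

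**5. Precision forgone.** Relative to independent infants, a pair model has information I = (1 − f) + f[a/(1+ρ) + (1−a)/(1−ρ)]. The fair comparator is the true variance of the planned estimator, so the gain is I × design effect.

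| f, ρ | a = 1/3 | a = 1/2 |
|---|---|---|
| 0.2, 0.2 | 1.022 × 0.987 = 1.009 | 1.008 × 1 = 1.008 |
| 0.3, 0.4 | 1.105 × 0.96 = 1.061 | 1.057 × 1 = 1.057 |
| 0.4, 0.6 | 1.350 × 0.92 = 1.242 | 1.225 × 1 = 1.225 |

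With a = 0.375 the central gain is 1.093 × 0.97 = 1.060. It is about 6% whichever split applies, worth roughly 0.06 × 164 ≈ 10 infants.

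**6. Aim 2 regressions.** With sibling correlation ρx in the measured predictor and ρy in the outcome, the design effect is about 1 + fρxρy, and the true type I error of a nominal 5% test is 2[1 − Φ(1.96/√DE)].

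- f = 0.2, both correlations 0.3: DE = 1.018, type I error 5.2%.
- f = 0.4, both correlations 0.6: DE = 1.144, type I error 6.7%.

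**7. If siblings were kept on the same gas (a = 1).** The text does not describe this; it is worked only to show why the rule should be confirmed. Design effect = 1 + fρ = 1.04 to 1.24 (central 1.12). Type I error would be 5.5-7.8%, and power at 82 per arm would be about 79% down to 71% (central 76%).

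**The case against.** A reader might infer that the trial's standard errors are wrong and its sample size too small. The documents do not support either. No standard error is stated anywhere. Randomisation is described infant by infant, and under that scheme the design effect is 1 or slightly below, so 82 per arm is adequate. By the plan's own rates, 268 × 0.82 × 0.80 ≈ 176 infants would be assessed against 164 needed, which would absorb a design effect of about 1.07. The inflated error rates and lost power in step 7 need siblings to be assigned together. The text does not describe that, so they cannot be charged to the plan as written.

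The twin share and correlations are also assumed. What matters is pairs in which both infants enrol, survive and are assessed, and the correlation left after adjustment for birth weight and socioeconomic status. Both push the gain down. The correlation must also be estimated from few pairs: 0.3 × 164 / 2 ≈ 25 in the central case. In Aim 2, the assigned gas is expected to drive part of the predictor, so split siblings may resemble each other less than assumed. Randomisation is said to follow an earlier publication, and any sibling rule there cannot be checked here.

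These points limit the size, not the direction. The plan still names an analysis that ignores siblings where a better one costs almost nothing.

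A reader might also suspect the primary model of being a Poisson fit with model-based variance. The plan names no such model, and that is not a sibling question.

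**Conclusion.** The omission is real and its effect is modest. For the primary outcome it is a matter of efficiency, not validity: about 6% more information at the central assumptions, about 1-24% over the range examined, and less after covariate adjustment or incomplete pairs. For the Aim 2 regressions it is a mild validity matter, with type I error of about 5.2-6.7% under the assumed correlations and only if siblings resemble each other on both the measurement and the outcome. The between-arm comparisons in Aim 2 behave like the primary test. The sample size stands as long as siblings are randomised individually. This is a free improvement.

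**What to change.** 1. Record a mother identifier for every infant.
2. Fit the primary relative-risk model as a log-link GEE with exchangeable correlation within mother and robust variance.
3. Use the same clustering for MDI, PDI, growth, and the Aim 2 comparisons and regressions, with the link suited to each outcome.
4. Confirm in the randomisation section that siblings are assigned individually. If practice differs and they share a gas, the ordinary standard error would be too small, and the 80% power should be restated with the assumed twin share and correlation.
5. Settle this before treatment codes are released, so that the choice cannot depend on the results.

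Cost: one data field and a few lines of analysis wording. No extra infants, visits or samples.

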**Specific Aim #1. Determine the effectiveness of iNO therapy on improving neurodevelopmental outcome in all O2-dependent premature infants having birth weights < 1500g.** We hypothesize that iNO therapy will improve neurodevelopmental outcome and growth at 18 months postconceptional age compared with placebo treated infants. In a double-blind, placebo-controlled clinical trial, premature infants being cared for in the Intensive Care Nursery at the University of Chicago Medical Center requiring any level of respiratory support will be randomized to receive iNO or placebo gas. Treatment will continue until infants either no longer require supplemental O2 therapy or reach 33 weeks gestational age, whichever comes first. At 18 months postconceptional age, infants will have neurodevelopment assessed and secondary clinical outcomes measured. The relative risks of abnormal neurodevelopmental outcome in the two groups will be compared. The roles played by variables known to independently affect neurodevelopmental outcome, as well as variables known to mediate abnormal neurodevelopmental outcomes will be statistically assessed.

**Specific Aim #2. Assess the mechanisms by which iNO therapy alters neurodevelopmental outcome in preterm infants.** We hypothesize that the amount of nitric oxide delivery to tissues will be positively correlated with neurodevelopmental outcome. Using routinely collected arterial and venous blood from infants in this study, measurements of nitrosylated hemoglobin and nitrite will be made. Arterial-venous differences will be calculated and mean differences compared across treatment groups. Arterial venous

differences will be regressed against neurodevelopmental outcome. Plasma levels of cyclic guanosine monophosphate (cGMP), the intracellular second messenger induced by nitric oxide will also be measured and levels regressed against neurodevelopmental outcome.

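### The adjustment sentence puts four intermediate variables into the primary-outcome model, and the plan never says which relative risk carries the conclusion

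*Combined protocol and SAP*

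**What the plan says.** Research Plan, Specific Aim #1, (xvi) Data analysis, commits to intent-to-treat and then states: "Primary outcomes will be analyzed with generalized linear models to obtain relative risks of primary outcome in the two groups". The next sentence is "Effects of potential confounders will be adjusted for in the model: birth weight, sex, socioeconomic status", and it continues "as well as for potential the intermediate variables: prolonged exposure to postnatal steroids, presence of chronic lung disease, severe IVH, or periventricular leukomalacia (PVL"). The label intermediate is therefore the plan's own.

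Two other places bear on the order of analysis. In the Specific Aims, Aim #1 says "The relative risks of abnormal neurodevelopmental outcome in the two groups will be compared", and a separate sentence says the roles of independent and mediating variables will be assessed. Section (xvii), on anticipated results, says "We further anticipate that these effects will persist after statistical adjustment for factors independently predisposing to abnormal neurodevelopmental outcome", and extends this to mediating factors.

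On size, (ix) takes 40% against 20% at 80% power and concludes that "82 babies are needed in each arm of the study". It then enlarges enrolment for deaths, "to ensure sufficient infants surviving to follow up", and again for loss to follow-up, reaching 268.

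**The concern.** Read literally, (xvi) describes one model for the primary outcome that contains variables which can arise after randomisation and which treatment may change. Conditioning on such a variable removes the part of the treatment effect that acts through it. Background 3 gives a reason to expect such a path: the investigators' previous trial reported markedly less serious intraventricular haemorrhage (IVH) and periventricular leukomalacia (PVL) with iNO, and the 793-infant multicentre trial reported a reduced combined endpoint of IVH, PVL and ventriculomegaly.

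Two analysts could both follow the plan and report different primary relative risks. One would report the contrast by randomised group. The other would report a contrast that leaves out any benefit acting through less brain injury or lung disease. If the two disagree on significance, nothing written beforehand says which one decides the trial.

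**Working it through.** **1. The plan's own figure.** Inputs from (ix): 40% and 20%, 80% power; equal allocation from (v). Alpha is not stated, so two-sided 5% is assumed. With pooled variance and mean proportion 0.30:

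n = [1.96 × √(2 × 0.30 × 0.70) + 0.8416 × √(0.40 × 0.60 + 0.20 × 0.80)]² / 0.20² = (1.2702 + 0.5323)² / 0.04 = 81.2, so 82 per arm.

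The stated figure is reproduced by a comparison of two proportions with no covariate, so the contrast the trial is sized for is the one between groups.

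**2. Who the 82 are.** Section (ix) adds infants for 18% mortality and then for 80% follow-up. From 268 enrolled, 268 × 0.80 × 0.82 = 175.8 are expected to be assessed, about 88 per arm. The target is thus the contrast among assessed survivors. Its power at 88 per arm is Φ[(0.20 × √88 − 1.96 × √0.42) / √0.40] = Φ(0.958) = 83%.

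**3. What conditioning on an intermediate does.** The documents give no mediator rates among the infants to be enrolled and no mediator-outcome effects, so this step is an illustration with assumed inputs. One binary mediator stands in for the four. Its rate is p0 on placebo and p1 = p0 × (1 − cut) on iNO, and it multiplies outcome risk by R. The group risks are held at 40% and 20%.

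- Placebo risk without the mediator: b0 = 0.40 / (1 − p0 + p0·R)
- Relative risk given the mediator: 0.20 / [b0 × (1 − p1 + p1·R)]

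With p0 = 20%:

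- No cut, any R: p1 = p0, so the result is 0.20 / 0.40 = 0.50.
- 25% cut, R = 2: b0 = 0.40 / 1.20 = 0.333; 0.20 / (0.333 × 1.15) = 0.52.
- 50% cut, R = 2: 0.20 / (0.333 × 1.10) = 0.55.
- 50% cut, R = 3: b0 = 0.40 / 1.40 = 0.286; 0.20 / (0.286 × 1.20) = 0.58.

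**4. Power at 88 per arm.** Simulation under the same assumptions (log-link Poisson model, robust standard errors, 5,000 replicates per scenario):

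| Scenario (p0 = 20%) | Adjusted RR | Power, mediator in model |
|---|---|---|
| no cut, R = 2 to 3 | 0.50 | 83% to 88% |
| 25% cut, R = 2 | 0.52 | 79% |
| 50% cut, R = 2 | 0.55 | 69% |
| 50% cut, R = 3 | 0.58 | 61% |

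Without the mediator, simulated power is 82% to 83% throughout, in line with step 2.

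**5. Is there a rule elsewhere?** Aim #1 in the Specific Aims compares the groups without naming a model. Section (xvii) states an expectation about results. Neither is a decision rule, and neither covers the case where the estimates differ.

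**The case against.** The best reply is that the plan is staged in substance. Section (xvi) speaks of models in the plural and gives the group relative risks first. Aim #1 separates comparing the groups from assessing mediators. Section (xvii) expects effects to persist after adjustment, which presupposes an effect already estimated. The sizing has no covariates. This favours reading the group comparison as primary and lowers the stakes, but it remains an inference against a sentence that says the adjustment is made in the model.

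The second reply also has force. The Specific Aims, Background 3 and the Aim #2 rationale all report that the earlier benefit persisted after adjustment for complications of prematurity, so the gap may be small. That cohort was ventilated and treated for up to 7 days; this trial adds non-ventilated infants and may treat until 33 weeks, so the size here stays unknown.

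Three stronger readings are tempting and not supported:

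- **That the trial is underpowered as planned.** Adjusted power stays near 80% in the mild assumed scenario, and there is no loss if iNO leaves the intermediates unchanged. The larger losses rest wholly on assumed inputs.
- **That iNO is shown to change all four variables.** The case is made for IVH and PVL. In the previous trial, the reported reduction in lung disease is stated together with death, the 793-infant trial found no overall difference in bronchopulmonary dysplasia, and no effect on postnatal steroids is reported.
- **That socioeconomic status should also leave the primary model.** Section (xv) says "Questionnaires assessing socioeconomic status and self report of racial ethnicity will be administered" in its account of the 18-month assessment. The plan nevertheless lists this variable as a confounder, and nothing suggests iNO changes it. The date of collection alone does not make it a mediator.

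**Conclusion.** The point holds as a defect of specification. Section (xvi), taken as written, puts self-described intermediate variables into the primary-outcome model, and no passage names the relative risk that decides the trial. The adjusted figure need not equal the contrast the trial is sized for. Attenuation needs two conditions together: iNO must reduce the intermediates, and the intermediates must raise the risk of abnormal outcome.

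The documents support the first condition for IVH and PVL, but they do not allow the gap to be sized. In the illustration it runs from nothing to an adjusted relative risk of 0.58 instead of 0.50, with power of about 61% instead of about 83%. That range assumes a single mediator at a 20% placebo rate, two-sided 5% alpha, and the plan's own mortality and follow-up figures. The missing primary label is certain; a loss of power is only possible. This is a free improvement, and it does not show that the design fails.

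**What to change.** Replace the adjustment sentence in (xvi) with:

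> The primary estimate is the relative risk of abnormal neurodevelopmental outcome by randomised group among infants assessed at 18 months, from a generalized linear model that contains no intermediate variables and adjusts only for the listed confounders (birth weight, the randomisation stratification factor; sex; socioeconomic status). Models that add postnatal steroids, chronic lung disease, severe IVH or PVL are secondary mediation analyses and do not replace the primary estimate.

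The cost is one sentence replaced by two, settled before unblinding. Sample size and data collection do not change, and every planned model is kept, including the mediator work in Aim #1.
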